Study Compound: Bimatoprost sustained-release (SR) biodegradable implants containing preservative-free AGN-192024 (bimatoprost)

Phase: 3

Study Objectives:

To evaluate the intraocular pressure (IOP)-lowering efficacy and safety of 2 dose strengths of Bimatoprost SR in patients with open-angle glaucoma (OAG) or ocular hypertension (OHT) after initial and repeated administrations

Clinical Hypotheses:

At least 1 dose strength (10 µg or 15 µg) of Bimatoprost SR will have an IOP-lowering effect that is noninferior to that of topically administered timolol maleate 0.5% (hereafter referred to as timolol) eye drops in patients with OAG or OHT following single and repeat administration.

Bimatoprost SR administered intracamerally in dose strengths of 10 µg or 15 µg will have an acceptable safety profile in patients with OAG or OHT following single and repeat administration.

Study Design

Structure: Phase 3, multicenter, randomized, masked, parallel-group comparison (2 dose strengths of Bimatoprost SR versus active control), repeat administration

Duration: Approximately 22 months, consisting of screening of up to 28 days before washout, washout period of up to 42 days before initial administration of study medication, 52-week treatment period, plus 8 months extended follow-up

Study Treatment Groups: Bimatoprost SR dose groups: 10 µg and 15 µg

Control: Timolol eye drops plus Sham needleless procedure (that involves touching the eye at the area of insertion with a needleless applicator).

Dosage/Dose Regimen: Patients will receive 1 of 2 dose strengths of Bimatoprost SR or Control treatment in the study eye on Day 1 (with repeat administration of the same dose strength or Sham at Week 16 and Week 32).

Bimatoprost SR-treated patients will receive intracameral administration of Bimatoprost SR in the study eye using a prefilled applicator. Timolol vehicle eye drops will be used twice daily (BID; in the morning and evening) to mask the treatment of patients receiving Bimatoprost SR in the study eye. The fellow eye will receive a Sham needleless procedure (hereafter called Sham administration or Sham administration procedure) plus topical timolol eye drops, BID. Control group patients will receive a Sham administration plus timolol in both eyes.

All patients will be masked to their treatment group. Treatment groups are shown in Table 1.

Table 1 Treatment Groups

Treatment	Study Eye Treatment	Fellow Eye Treatment
Bimatoprost SR 10 µg	Dose strength: 10 µg	Sham administration procedure
	Eye drops: Vehicle BID	Eye drops: Timolol BID
Bimatoprost SR 15 µg	Dose strength: 15 µg	Sham administration procedure
	Eye drops: Vehicle BID	Eye drops: Timolol BID
Control	Sham administration procedure	Sham administration procedure
	Eye drops: Timolol BID	Eye drops: Timolol BID

BID = twice daily

The patients will begin self-administration of the study-provided eye drops (vehicle or timolol) in both eyes, starting with the evening dose on the first administration (Bimatoprost SR or Sham administration) day visit. Patients will continue self-administration of the study-provided eye drops in the morning (08:00 ± 1 hour) and in the evening (20:00 ± 1 hour) approximately 12 hours apart throughout the study, with the exception of the morning of a subsequent visit, on which the morning eye drop administration will be performed at the study site.

Randomization/Stratification: Randomization to treatment groups will use a 1:1:1 ratio (Bimatoprost SR 10 µg:Bimatoprost SR 15 µg:Control). Randomization will be stratified by baseline study eye Hour 0 IOP (≤ 25 mm Hg or > 25 mm Hg).

Visit Schedule: Patients who complete the entire study without receiving nonstudy IOP-lowering medication in both eyes will have a minimum of 25 visits and 6 phone calls. [REDACTED]

[REDACTED]

Patients who have not received nonstudy IOP-lowering medication (prohibited prior to Week 52) in both eyes will receive a repeat administration of Bimatoprost SR (or Sham administration in Control group study eyes and all fellow eyes) at the Week 16 and Week 32 visits as indicated. Administration should not occur if the investigator believes that there are any safety concerns. Patients who have received nonstudy IOP-lowering medication in both eyes will be followed for at least 12 months following the last administration of Bimatoprost SR or Sham, at which time they may exit early at the investigator’s discretion.

Study Population Characteristics

Number of Patients: Approximately 600 patients will be enrolled in the study.

Condition/Disease: Patients with OAG (primary OAG, pseudoexfoliative glaucoma, or pigmentary glaucoma) or OHT who require IOP-lowering medications in both eyes. The eye that meets the entry criteria will be selected as the study eye. If both eyes meet the entry criteria, the eye with the higher IOP at baseline Hour 0 will be selected as the study eye. If both eyes have the same IOP at Hour 0, then the right eye will be designated as the study eye.

Key Inclusion Criteria:

- [REDACTED]
- Diagnosis of either OAG (ie, primary, pseudoexfoliation, or pigmentary glaucoma) or OHT in each eye and both eyes require IOP-lowering treatment (Note: diagnosis does not have to be the same in both eyes)
- [REDACTED]

Approval Date: 16-Mar-2017

- [REDACTED]
- [REDACTED]
- [REDACTED]
- [REDACTED]
- [REDACTED]
- [REDACTED]
- [REDACTED]
- [REDACTED]

Key Exclusion Criteria:

- The following surgical history:
 - a. History or evidence of complicated cataract surgery in the study eye: eg, surgery resulting in complicated lens placement (such as anterior chamber intraocular lens implant [IOL], sulcus IOL, aphakia, etc) or intraoperative complications (such as a posterior capsular tear [with or without vitreous loss], substantial iris trauma, etc)

Note: history of uncomplicated cataract surgery is not an exclusion.
 - b. History of phakic IOL insertion for refractive error correction in the study eye
- [REDACTED]
- [REDACTED]

Response Measures

Efficacy: Intraocular pressure measured by Goldmann applanation tonometry

Safety: Adverse events: [REDACTED]

General Statistical Methods and Types of Analyses:

The intent-to-treat population (ITT) is defined as all randomized patients and will be used for demographic and efficacy analyses. The per protocol (PP) population will consist of the subset of the ITT population with no protocol deviations affecting the primary efficacy analysis and will be used to confirm the primary efficacy analysis. A list of patients excluded from the PP population will be finalized prior to database lock. The safety population is defined as all patients who received study drug treatment and will be used for safety analyses. Analyses in the ITT population will be based on the treatment to which a patient was randomized, and analyses in both the PP and safety populations will be based on the actual treatment a patient received.

Continuous variables will be summarized by descriptive statistics including sample size, mean, standard deviation, median, minimum, and maximum. Categorical variables will be summarized by frequency and percentage.

The primary efficacy variable is study eye time-matched IOP change from baseline. Mean IOP change from baseline will be compared between each Bimatoprost SR dose strength and timolol for each hour (Hours 0 and 2) using the ITT population. The comparisons at Week 12 will be considered the primary analysis.

[figure not shown]
Intraocular pressure change from baseline will be analyzed using a mixed-effects model repeated measures (MMRM) approach. The model will include IOP time-matched change from baseline as the response variable and treatment, timepoint (Hours 0 and 2 at each visit of Weeks 2, 6, and 12), treatment-by-timepoint interaction, and baseline IOP stratification as fixed effects. Unstructured covariance matrix will be used for repeated measures on the same patient; if the model with unstructured covariance matrix fails to converge, multiple imputation (MI) will be implemented before MMRM.

Within the framework of this model, the mean difference between each Bimatoprost SR dose strength and timolol (Bimatoprost SR minus timolol) and the corresponding 2-sided 95% confidence interval will be provided for each hour (Hours 0 and 2) at each visit. The formal noninferiority test will be performed at Week 12 for each Bimatoprost SR dose strength versus timolol using a noninferiority margin of 1.5 mm Hg. A gatekeeping procedure will be used to control the overall type I error rate at the 0.05 level for each hour at Week 12, testing Bimatoprost SR 15 µg against timolol first and followed by the comparison between Bimatoprost SR 10 µg and timolol. The test of Bimatoprost SR 10 µg versus timolol for a given hour at Week 12 is valid only if the noninferiority of Bimatoprost SR 15 µg to timolol is demonstrated for the same timepoint. Bimatoprost SR 15 µg (or 10 µg) will be declared noninferior to timolol if the upper limit of the 95% confidence interval is ≤ 1.5 mm Hg for both Hours 0 and 2 at Week 12.

[figure not shown]
For the United States Food and Drug Administration (US FDA), the primary efficacy variable will be the study eye IOP. The primary analysis will be based on Weeks 2, 6, and 12 using the ITT population. Specifically, the following analysis will be performed: IOP will be analyzed using an MMRM approach based on the same model as described for the primary efficacy analysis of time-matched IOP change from baseline. Within the framework of this model, the mean difference between each Bimatoprost SR dose strength and timolol group and the corresponding 95% confidence interval will be provided for each hour (Hours 0 and 2) and each visit (Weeks 2, 6, and 12). A gatekeeping procedure will be used to control the overall type I error rate at the 0.05 level for each timepoint, testing Bimatoprost SR 15 µg against timolol first and followed by the comparison between Bimatoprost SR 10 µg and timolol. The test for Bimatoprost SR 10 µg versus timolol for a given hour at a visit is valid only if the noninferiority of Bimatoprost SR 15 µg to timolol has been demonstrated for the given timepoint. Each Bimatoprost SR dose strength that shows noninferiority to timolol at all 6 timepoints with a 1.5 mm Hg margin (ie, the upper limit of the 95% confidence interval is ≤ 1.5 mm Hg) will be declared clinically noninferior to timolol if the upper limit of the 95% confidence interval is ≤ 1.0 mm Hg for 3 or more timepoints.

Adverse events will be coded using the Medical Dictionary for Regulatory Activities (MedDRA) and will be summarized for all events regardless of causality and for treatment-related adverse events. Ocular adverse events and safety variables will be tabulated by study eye and fellow eye within each treatment dose strength or group, and nonocular safety variables will be summarized by patient.

[figure not shown]
Sample Size Calculation: The sample size calculation is based on the primary efficacy analysis of the IOP for US FDA review because the sample size based on the primary efficacy analysis for other regions is expected to be smaller. Based on simulations, a sample size of 540 patients (180 per group) will provide approximately 95% and 81% power to show noninferiority (NI) of Bimatoprost SR 15 µg and Bimatoprost SR 10 µg, respectively, to timolol at all 6 scheduled timepoints based on an NI margin of 1.5 mm Hg and at 3 or more timepoints based on an NI margin of 1.0 mm Hg. Assuming a premature discontinuation rate of 10% within 12 weeks (before the primary database lock), approximately 600 patients (200 per group) are to be enrolled into this study.

[figure not shown]
Approval Date: 16-Mar-2017

[figure not shown]
Approval Date: 16-Mar-2017

[figure not shown]
Approval Date: 16-Mar-2017

Approval Date: 16-Mar-2017

[figure not shown]

Approval Date: 16-Mar-2017

[figure not shown]

Approval Date: 16-Mar-2017

[figure not shown]

Approval Date: 16-Mar-2017

Approval Date: 16-Mar-2017

Approval Date: 16-Mar-2017

1. Background and Clinical Rationale

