The investigator is strongly encouraged not to use prohibited medications as outlined in Section 4.5.2. In order to maintain masking in the event that nonstudy IOP-lowering medications (prohibited prior to Week 52 unless required for a safety reason and attested to by the investigator) are administered, if a patient is started on a nonstudy IOP-lowering medication in only one eye, the patient will continue to use the study-provided eye drops in that eye as directed. The nonstudy IOP-lowering medication will be prescribed by the investigator according to local standard of care practices and used in addition to the study-provided eye drops in that eye. The eye not receiving a nonstudy IOP-lowering medication will continue to receive the study-provided eye drops as directed. If the eye receiving the nonstudy IOP-lowering medication is a Bimatoprost SR study eye, the eye will receive Sham administration on the administration day(s). If the eye receiving the nonstudy IOP-lowering medication is a Control group study eye or a fellow eye, the eye will continue to receive Sham administration on the administration day(s). If both eyes are receiving nonstudy IOP-lowering medications, the patient will discontinue use of the Allergan

study-provided eye drops and will not receive additional Bimatoprost SR or Sham administration (see Section 5.6.1). However, as described in Section 8.8, the patient will still remain in the study and be followed for 12 months following their last administration of Bimatoprost SR or Sham.

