5.6.1 Treatment Regimen/Dosage Adjustments

Patients who have received nonstudy topical IOP-lowering medication (prohibited before Week 52 unless required for safety reasons due to inadequate IOP control and attested to by the investigator) in a Bimatoprost SR study eye will receive Sham administration in that eye on the Bimatoprost SR repeat administration day(s). Patients who have received nonstudy topical IOP-lowering medication in a fellow eye or a Control Group study eye will continue to receive Sham administration in that eye on the administration day(s).

Patients who have received nonstudy IOP-lowering medication in both eyes will not undergo Bimatoprost SR administration or Sham administration in either eye.

Patients who use nonstudy IOP-lowering medication (prohibited before Week 52 unless required for safety reasons due to inadequate IOP control and attested to by the investigator) in only one eye will be followed for the duration of the study. If used in both eyes, patients will be followed at minimum for 12 months after the last administration of Bimatoprost SR or Sham. Patients using nonstudy IOP-lowering medications in both eyes prior to the Week 16 or Week 32 Administration Day will not attend the administration visit(s), nor will they attend the Day 2, Days 4 and 8 (phone call), or 2-week visits (ie, Weeks 2, 18, and 34) following an administration. They would continue the schedule at Week 22 or Week 38, as appropriate for the administration cycle.

Patients who have received nonstudy IOP-lowering medication in both eyes before the time of the Month 14 visit are not required to attend the Month 14 or 18 visits unless the visit is 12 months after their last injection or Sham, at which time the patient may exit early and should complete all Month 20/Exit visit examinations. Patients who have received nonstudy IOP-lowering medication in both eyes by the time of the Month 16 visit are not required to attend the Month 18 visit, unless that visit is 12 months after their last injection or Sham, at which time the patient may exit early and should complete all Month 20/Exit visit examinations.

For patients who have not received nonstudy IOP-lowering medications by the time of study discontinuation or completion, poststudy evaluations regarding the need for IOP-lowering medications should be conducted according to the treating physician's clinical opinion.

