5.10 Retreatment

Administration of Bimatoprost SR will occur at fixed intervals of 16 weeks, up to a total of 3 administrations. Patients will be readministered the Bimatoprost SR dose strength to which they were randomized unless in the investigator's opinion it would not be in the best interest of the patient to readminister Bimatoprost SR based on previous adverse events or safety concerns. Patients who have been treated with nonstudy IOP-lowering medication in only one eye will still attend administration visits; if the treated eye is the Bimatoprost SR study eye, the patient will receive a Sham administration in that eye. Control group study eyes and fellow eyes that have been treated with nonstudy IOP-lowering medications will continue to receive Sham administrations. Patients who have been treated with nonstudy IOP-lowering medication in both eyes will not attend the Administration Day visits, nor will they attend the Day 2, Days 4 and 8 (phone call), or the 2-week visits (ie, Weeks 2, 18, and 34) following an administration.

6. Response Measures and Summary of Data Collection Methods

Detailed information on equipment and methodology to be used is provided in the Protocol Procedure Manual.

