7.3.1 Primary Efficacy Analyses

The primary efficacy variable is the study eye time-matched IOP change from baseline. Mean IOP change will be compared between each Bimatoprost SR dose strength and the timolol group for each hour (Hours 0 and 2) using the ITT population. The comparisons at Week 12 will be considered the primary analysis.

The null and alternative hypotheses for the comparison between a given Bimatoprost SR dose strength and timolol at each hour of Week 12 are:

- Null hypothesis: the difference in mean IOP change from baseline between the given Bimatoprost SR dose strength and timolol (Bimatoprost SR minus timolol) is > 1.5 mm Hg.
- Alternative hypothesis: the difference (Bimatoprost SR minus timolol) in mean IOP change from baseline between the given Bimatoprost SR dose strength and timolol is ≤ 1.5 mm Hg.

Intraocular pressure change from baseline will be analyzed using a mixed-effects model repeated measures (MMRM) approach. The model will include IOP time-matched change from baseline as the response variable and treatment, timepoint (Hours 0 and 2 at each visit of Weeks 2, 6, and 12), treatment-by-timepoint interaction, and baseline IOP stratification as fixed effects. Unstructured covariance matrix will be used for repeated measures on the same patient; if the model with unstructured covariance matrix fails to converge, multiple imputation (MI) will be implemented before MMRM. The details of the model specifications will be provided in the analysis plan.

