4.0 INTRODUCTION

This statistical analysis plan (SAP) provides a more technical and detailed elaboration of the statistical analyses of the efficacy and safety data for Study 192024-091. Specifications of tables, figures, and data listings are contained in a separate document.

Study 192024-091 is a Phase 3, multicenter, randomized, masked, parallel-group comparison, active-controlled, repeat administration study in patients at least 18 years of age who have been diagnosed with open-angle glaucoma (OAG) or ocular hypertension (OHT).

The length of the study will be approximately 22 months for each patient, consisting of screening of up to 28 days before washout, washout period of up to 42 days before initial administration of study medication, 52-week treatment period, plus 8 months extended follow-up. Signed informed consent from the patient or the patient's legally authorized representative will be obtained before any study-related procedures are begun. All patients who provide informed consent will be assigned a subject number. Patients meeting all inclusion and no exclusion criteria will be randomized in a 1:1:1 ratio to receive 1 of 2 dose strengths of Bimatoprost SR treatment (Bimatoprost 10 µg or 15 µg plus vehicle twice daily [BID] eye drops) or control treatment (Sham administration procedure plus timolol BID eye drops) in the study eye on Day 1. The randomization will be further stratified by baseline study eye Hour 0 IOP (≤ 25 mm Hg or > 25 mm Hg). Patients who have not received non-study IOP-lowering medication in both eyes will receive a repeat administration of Bimatoprost sustained release (SR) or control treatment in the study eye at the Week 16 and Week 32 visits.

[figure not shown]
All patients will be masked to their treatment group. Treatment groups are shown as follows:

Treatment	Study Eye Treatment	Fellow Eye Treatment
Bimatoprost SR 10 µg	Dose strength: 10 µg Eye drops: Vehicle BID	Sham administration procedure Eye drops: Timolol BID
Bimatoprost SR 15 µg	Dose strength: 15 µg Eye drops: Vehicle BID	Sham administration procedure Eye drops: Timolol BID
Control	Sham administration procedure Eye drops: Timolol BID	Sham administration procedure Eye drops: Timolol BID

[figure not shown]
BID = twice daily

[figure not shown]

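### For a Bimatoprost SR patient rescued in the study eye only, the Protocol Summary and SAP 4.0 call for another implant at Weeks 16 and 32, while Protocol 5.3, 5.6.1 and 5.10 call for Sham

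*Protocol*

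**What the plan says.** Below, rescue means nonstudy IOP-lowering medication.

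**Protocol Summary and SAP Introduction.** The Protocol Summary, under Visit Schedule, describes who is treated again at Weeks 16 and 32: "Patients who have not received nonstudy IOP-lowering medication (prohibited prior to Week 52) in both eyes will receive a repeat administration of Bimatoprost SR". Its parenthesis assigns Sham to Control study eyes and to all fellow eyes, and to no other eye. SAP 4.0 uses the same condition and attaches it to the study eye: "Patients who have not received non-study IOP-lowering medication in both eyes will receive a repeat administration of Bimatoprost sustained release (SR) or control treatment".

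**Protocol body.** Three sections address the rescued Bimatoprost SR study eye directly:

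- Section 5.6.1 says that patients given rescue "in a Bimatoprost SR study eye will receive Sham administration in that eye on the Bimatoprost SR repeat administration day(s".
- Section 5.3 says: "If the eye receiving the nonstudy IOP-lowering medication is a Bimatoprost SR study eye, the eye will receive Sham administration on the administration day(s".
- Section 5.10, on patients rescued in one eye only, says: "if the treated eye is the Bimatoprost SR study eye, the patient will receive a Sham administration in that eye".

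For bilateral rescue, Section 5.6.1 says: "Patients who have received nonstudy IOP-lowering medication in both eyes will not undergo Bimatoprost SR administration or Sham administration in either eye".

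**The concern.** The Summary and SAP 4.0 make repeat dosing depend on whether both eyes have been rescued. The body sections make it depend on whether the Bimatoprost SR study eye itself has been rescued. A patient rescued in that eye alone falls between the two conditions and is assigned an implant by one and Sham by the other.

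The difference is whether an intracameral implant is injected. It arises only in the two Bimatoprost SR arms, because a Control study eye never receives an implant under any reading.

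It also reaches the analysis. The objective and both clinical hypotheses cover repeat administration, and several SAP outputs are defined by who received which administration. SAP 4.0 does not acknowledge that a Bimatoprost SR study eye can receive Sham at all.

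**Working it through.** The plan states no figure here, so the check is a comparison of text.

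**1. Four cases for a Bimatoprost SR patient, study eye at Week 16 or 32**

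| Rescue so far | Summary and SAP 4.0, read literally | Protocol 5.3, 5.6.1, 5.10 |
|---|---|---|
| None | Repeat implant | Repeat implant |
| Fellow eye only | Repeat implant | Repeat implant not withdrawn |
| Study eye only | Repeat implant | Sham |
| Both eyes | Outside the condition for repeat administration | Neither procedure |

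The two sets of passages agree in three cases and conflict in one. Within each set the passages agree with one another.

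**2. Prior or current use**

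Section 5.3 speaks of an eye *receiving* rescue, 5.6.1 of patients who *have received* it, and 5.10 of patients who *have been treated*. Section 5.6.1 also switches to *using* when it says who skips the administration visits. For rescue that is still in use on the administration day, all three sections lead to the same result. For rescue that has been stopped, no visible passage says whether the rule still applies.

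**3. What is not affected**

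- Protocol 7.3.1: "The comparisons at Week 12 will be considered the primary analysis". The US FDA analysis uses Weeks 2, 6 and 12. The first repeat administration is at Week 16, so neither primary analysis depends on this rule.
- Protocol 7.2 and SAP 10.1 exclude an eye's IOP from summaries and analyses once rescue has started in it. Whether a rescued eye is then given an implant or Sham, its later IOP is not in the efficacy results.

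**4. What is affected**

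- SAP 7.0 defines cycle completers as patients who received an injection in that cycle.
- SAP 9.1 tabulates Bimatoprost SR or Sham treatment of the study eye by number of administrations within each treatment group. The visible text does not separate Sham from implant within a Bimatoprost SR arm.
- SAP 11.0 bounds Cycles 1 to 3 by injection dates and limits extended follow-up to patients with three injections.

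In these definitions the word injection has to include Sham for the Control arm, or Control would have no cycles. The SAP does not say whether a Sham given to a Bimatoprost SR study eye counts in the same way. If it counts, eyes with one implant and eyes with two are pooled in Cycle 2. If it does not, these patients fall outside the Cycle 2 or Cycle 3 definitions.

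**5. Size**

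About 200 patients per group (Protocol 4.1) gives 2 × 200 = 400 in the Bimatoprost SR arms. The documents give no rescue rate. Each 1% with study-eye-only rescue before an administration visit is 0.01 × 400 = 4 eyes. Under an assumed range of 2% to 15%, the two rules would give different instructions for 0.02 × 400 = 8 to 0.15 × 400 = 60 eyes per visit. That is the number exposed to the conflict under the assumption, not an estimate of eyes treated differently.

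**The case against.** The strongest reply is that the operative text is clear. Three body sections state the outcome for exactly this patient and agree. The Summary is condensed, qualifies the visits with an as-indicated phrase, and tells sites not to administer where the investigator sees a safety concern. The SAP Introduction does not instruct sites. Protocol 5.5 has sites obtain kit numbers from the IV/WRS, which may already apply one rule, and the relevant visit-schedule text is redacted.

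Much of this stands, and it limits what can be claimed. A reader might infer that sites are free to implant or to give Sham, or that practice will differ between sites. The documents do not show that; the practical risk is reliance on the Summary alone. The reply does not remove the contradiction, however. The Summary lists the eyes that get Sham and leaves this one out. The as-indicated phrase states no exception, and the safety clause is at the investigator's discretion whereas the body rule is automatic.

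It could also be argued that the Summary's condition means rescue in neither eye, which would leave one-eye rescue unaddressed. The same paragraph then treats patients rescued in both eyes as the contrasting group, so the not-both reading is the natural one. Under either reading the study-eye exception is absent.

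A reader might also see a third rule in the present tense of Section 5.3, so that Sham would apply only during current use. The text does not support this. The passage in 5.3 is triggered when a patient starts rescue, and for bilateral rescue it refers to 5.6.1. What remains is a gap: nothing visible covers rescue that has been stopped.

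**Conclusion.** The contradiction is real and narrow. There are two stated rules, and they conflict only for a Bimatoprost SR patient rescued in the study eye alone. The tense variation is a secondary ambiguity, not a third rule.

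A reader might infer a threat to the primary result, or to the estimated duration of IOP lowering. Neither follows, because repeat dosing starts after Week 12 and IOP after rescue is excluded for that eye. The consequence is confined to whether a rescued eye is injected again and to the completer, exposure and by-cycle safety summaries in the Bimatoprost SR arms. Protocol 7.1 analyses safety by actual treatment, which helps, but it does not say how an eye with a mixture of implant and Sham is classified by cycle.

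The number of eyes is unknown; the 8 to 60 above rests wholly on an assumed rate. The conclusion assumes that the redacted schedule text and the IV/WRS specification, which cannot be seen, do not already settle the matter. The point should be corrected because it governs an invasive procedure and costs little to repair. This review takes no position on which clinical rule is right.

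**What to change.** 1. Reconcile the Protocol Summary (Visit Schedule) and SAP 4.0 with Protocol 5.3, 5.6.1 and 5.10, so that all five places state one rule in the same words. The rule should say which eye's rescue triggers it, and whether any prior use or only current use on the administration day counts. Use the same terms for the both-eyes condition. The clinical team decides which rule stands.
2. Confirm that the IV/WRS kit request at Weeks 16 and 32 applies that rule.
3. In SAP 7.0, 9.1 and 11.0, define injection explicitly, and report Bimatoprost SR-arm study eyes given Sham separately from those given an implant at each administration.

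The cost is wording changes in the five places, clearer definitions and an extra split in the SAP tables, and one IV/WRS check. No visits or patients are added.
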